2.7.5 Renal events

Summary of treatment emergent renal event overview data by treatment will be presented. All renal event overview data will be listed.

2.7.6 Liver events

[figure not shown]
[figure not shown]
Summary of treatment emergent liver event overview data by treatment will be presented. All liver event overview data will be listed.

[figure not shown]
2.8 Pharmacokinetic endpoints

[figure not shown]
Not Applicable

[figure not shown]
2.9 PD and PK/PD analyses

[figure not shown]
Not Applicable

2.12 Interim analysis

No interim analysis for efficacy is planned in this study. An independent, external DMC has been set up to review safety data (including specific safety summaries for adolescent participants) for this trial. No statistical adjustment will be made to the final analysis.

3 Sample size calculation

The primary objective is to demonstrate that QAW039 150 mg is superior to placebo in pre-dose FEV1 following 12 weeks of post-baseline treatment. A difference of 112 mL in pre-dose FEV1 during treatment was assumed, which is similar to the model-averaged effect seen in

study QAW039A2206. The standard deviation (SD) of 380 mL and between-visit correlation for pre-dose FEV1 was based on study QAW039A2206 in a similar population. A treatment discontinuation rate of 15% was assumed based on QAW039A2206 and it was assumed that half of the patients discontinuing study treatment would have week 12 FEV1 values. Simulations were used to determine the sample size due to the complex J2R missing data imputation approach for the primary analysis.

Under the outlined assumptions, a sample size of 650 patients (325 per arm) would be needed to have 90% power to observe a statistically significant difference between QAW039 and placebo at the two-sided 5% significance level in the primary analysis as shown in [Table 3-1](#). The table also shows the sensitivity of the power to deviations from the assumptions.

Table 3-1 Result of power simulations for the primary variable

Treatment effect (mL)	Discontinuation rate	Sample size	Power
112	15%	650	90.3
112	20%	650	85.9
100	15%	650	80.9

Based on 10,000 simulated trials per scenario and 250 multiple imputations for each trial. Simulations were conducted using SAS/STAT® 13.1 software, Version 9.4 of the SAS System for Linux.

Power for the secondary objectives

If statistical significance is achieved in the primary test, the tests for the secondary variables will be performed. The local significance level for each secondary null hypothesis will be determined based on the closed testing procedure shown in [Figure 2](#).

As differences in FEV1 to placebo for QAW039 150 mg once daily and montelukast 10 mg once daily appeared to be of similar magnitudes in study QAW039A2206, the power calculations for the two secondary objectives (change from baseline in daytime asthma symptoms and change from baseline in total daily SABA use) are based on the assumptions from the results of two studies comparing montelukast 10 mg once daily with placebo ([Reiss et al 1998](#), [Malmstrom et al 1999](#)). These studies suggest an averaged difference of 0.26 for change from baseline in daytime asthma symptoms between montelukast and placebo after 12 weeks of treatment and a SD of 0.94. The two studies also suggest an averaged difference of -1.34 point difference in the change from baseline in the number of daily SABA puffs between montelukast and placebo with a standard deviation of 3.82. We assume a clinically important true improvement of at least 0.5 in AQLQ+12 after 12 weeks of treatment for patients that remain on treatment and a standard deviation (SD) of 1. As shown in [Table 3-2](#) all secondary endpoints have an adequate conditional power once the primary null hypothesis has been rejected, but will each have an even higher conditional power once the null hypotheses relating to the other secondary variables have been rejected.

Table 3-2 Power simulations for secondary variables

	Daytime asthma symptoms	Total daily rescue medication use	AQLQ+12
Difference of effect (δ)	-0.26	-1.34 number of puffs	0.5
SD (σ)	0.94	3.82 number of puffs	1
Local two-sided significance level once primary null hypothesis is rejected	0.0245	0.0245	0.001
Power	74%	97%	98%
Local two-sided significance level once primary and the other two secondary hypotheses are rejected	0.05	0.05	0.05
Power	83%	98%	> 99%

[figure not shown]
Power statements are based on 10,000 simulated trials per scenario and 250 multiple imputations using a jump-to-reference approach for each simulated trial. Simulations were conducted using SAS/STAT® 13.1 software, Version 9.4 of the SAS System for Linux. We assumed a treatment discontinuation rate of 15% with half of the patients discontinuing from study treatment completing the trial. The correlation structure was assumed the same as for the primary endpoint. Abbreviation: AQLQ+12 (asthma quality of life questionnaire for 12 years and older).

[figure not shown]
4 Change to protocol specified analyses

- Section 9.2 in the study protocol states that the age of the patient will be calculated from the date of birth to date of Visit 1. However, since date of birth is not captured on the CRF page and age (in years) at the time of informed consent is entered into CRF, there is no need to re-calculate age.
- Shift tables relative to the normal reference ranges to summarize the on-treatment change from baseline to post-baseline for each laboratory parameter or ECG parameter or vital sign assessments will not be presented.
- Study protocol defines treatment emergent adverse events as those events starting on or after the time of the first intake of study drug and until the day after the last intake of study drug. However, in order to maintain consistency with the submission documents, for analysis purposes the following updated definitions are considered:
AEs starting on or after the time of the first intake of study drug and not later than 7 days (30 days in the case of a serious AE) after the last intake of study drug will be classified as a TEAE.
- Added the responder analysis for AQLQ improvement
- Added more details to liver function tests including eDISH plot
- Added analysis for renal events and liver events according to project level alignment
- The following analyses, though pre-specified in the protocol, may not be critical for decision making purposes and hence will be reported outside of CSR:

- 

- In protocol 9.4.4, supportive analysis for the primary endpoint based on other missing data imputation approaches: pattern mixture approach combining the jump to reference and missing at random approaches by distinguishing reasons for discontinuation of treatment and retrieved dropout imputation approach.
- In protocol Section 9.4.4, subgroup analyses for BMI, number of exacerbations in the previous year, ACQ tertiles, [REDACTED].
- Summaries on post-treatment discontinuation events to be produced for adverse events and serious adverse events by system organ class and preferred term.

6 Appendix

This appendix gives details about statistical methods in addition to the report text. All analyses will be performed by using SAS Version 9.4.

Note: The SAS version that will be actual on the NOVARTIS platform at the time when the study is completed will be stated here.

6.1 Imputation rules

6.1.1 Study drug

Missing/partial start date or end date of study treatment will not be imputed.

6.1.2 AE date imputation

Rules for imputing AE end date or start date will be provided in Programming Dataset Specification (PDS) document in details.

6.1.3 Concomitant medication date imputation

Rules for imputing concomitant medication start or end dates will be provided in Programming Dataset Specification (PDS) document in details.

6.1.3.1 Prior therapies date imputation

Rules for imputing the prior therapies end date or start date will be provided in Programming Dataset Specification (PDS) document in details.

6.1.3.2 Post therapies date imputation

Rules for imputing the post therapies end date or start date will be provided in Programming Dataset Specification (PDS) document in details.

6.2 AEs and Concomitant medications coding/grading

The MedDRA version which will be available at the time of database lock, will be used for the coding purpose of the adverse events. For coding purpose of the concomitant medications, the available WHO-DD (World Health Organization- Drug Dictionary) version at the time of database lock will be used.

6.3 Visit remapping and assessment windows

If a scheduled visit did not occur, the data from the treatment discontinuation or study discontinuation visit may be used as the data from the scheduled visit, if the treatment discontinuation or study discontinuation visit occurred closer to the planned study day of the missing scheduled visit than to the planned study day of any other scheduled visit. In this case, the treatment discontinuation or study discontinuation visit will be treated as the scheduled visit for the purpose of all analyses so that no missing data imputation will be necessary. Otherwise, the data from any scheduled visit that did not occur will be dealt with like any other missing data. If the treatment discontinuation or study discontinuation visit is not re-mapped to any scheduled visit, it will be treated as an unscheduled visit that does not appear in by-visit summaries.

6.4 Laboratory parameters derivations

The following table shows the criteria for clinically notable laboratory values. Not all parameters have notable criteria defined.

Table 6-4-1 Direction of interest for worst case value for laboratory parameters

Laboratory Parameter	Direction of interest for worst case value
A. Hematology	
Basophils	High
Eosinophils	High
Hematocrit	Low
Hemoglobin	Low
Lymphocytes	Low and high
Monocytes	High
Neutrophils	Low and high
Platelets	Low and high
RBC	Low
WBC total	Low and high
B. Chemistry	
Albumin	Low
Sodium	Low and High
Alkaline Phosphatase	High
ALT/SGPT	High
AST/SGOT	High
Bilirubin Total	High
Blood Urea Nitrogen (BUN)	High
CPK	High
Creatinine	High
Gamma GT	High
Glucose	Low and high
Potassium	Low and high
Uric acid	High

Table 6-4-2 Clinical notable criteria for selected laboratory tests

Laboratory parameter (unit)	Bound for notably low values	Bound for notably high values
Hematology		
Hematocrit (v/v)		
Male aged 12-17	0.34	
Male aged 18-65	0.37	
Male aged >=66	0.34	
Female aged 12-65	0.32	
Female aged >=66	0.31	

Laboratory parameter (unit)	Bound for notably low values	Bound for notably high values
Hemoglobin (g/L)		
Male aged 12-17	100	
Male aged >=18	110	
Female	95	
Thrombocytes (x10E ⁹ /L)	75	700
WBC's (x10 ⁹ /L)	2.8	16.0
Chemistry		
Alkaline Phosphatase (IU/L)	-	3xULN
Total Bilirubin (µmol/L)	-	34.2
Creatinine (µmol/L)		176.8
Potassium (mmol/L)	3	6
Glucose (mmol/L)	2.78	9.99
ALT/SGPT (U/L)	-	3 x ULN
AST/SGOT (U/L)	-	3 x ULN
BUN/ Urea (mmol/L)		9.99
Sodium (mmol/L)	125	160
Gamma GT (U/L)		3 x ULN
CPK (IU/L)		4 x ULN
Urinalysis		
Dipstick blood		≥ 2+
Dipstick glucose		≥ 2+
Dipstick leukocytes		≥ 2+
Dipstick protein		≥ 2+

v = volume, ULN = upper limit of normal

Table 6-4-3 Notable liver function test values

Criterion
ALT > 3 x ULN ALT > 5 x ULN ALT > 8 x ULN ALT > 10 x ULN ALT > 20 x ULN
ALT or AST > 3 x ULN ALT or AST > 5 x ULN ALT or AST > 8 x ULN ALT or AST > 10 x ULN ALT or AST > 20 x ULN
Total Bilirubin > 1 x ULN Total Bilirubin > 1.5 x ULN Total Bilirubin > 2 x ULN Total Bilirubin > 3 x ULN
ALP > 1.5 x ULN ALP > 2 x ULN ALP > 3 x ULN ALP > 5 x ULN
ALT or AST > 3 x ULN and Total Bilirubin > 1.5 x ULN ALT or AST > 3 x ULN and Total Bilirubin > 2 x ULN ALT or AST > 5 x ULN and Total Bilirubin > 2 x ULN ALT or AST > 8 x ULN and Total Bilirubin > 2 x ULN ALT or AST > 10 x ULN and Total Bilirubin > 2 x ULN ALT or AST > 20 x ULN and Total Bilirubin > 2 x ULN
ALP > 3 x ULN and Total Bilirubin > 2 x ULN ALP > 5 x ULN and Total Bilirubin > 2 x ULN
ALT or AST > 3 x ULN and Total Bilirubin > 2 x ULN and ALP ≤ 2 x ULN (Hy's law)
ALT or AST > 3 x ULN and (nausea or vomiting or fatigue or general malaise or abdominal pain or (rash and eosinophilia))*

ALT=alanine aminotransferase; AST=aspartate aminotransferase; ALP=alkaline phosphatase; ULN=upper limit of normal. *Based on the signs/symptoms information as recorded on the liver events eCRF, not the adverse events eCRF.

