12. Patients who have an asthma exacerbation requiring systemic corticosteroids, hospitalization or emergency room visit during the screening or placebo run-in periods. Patients who experience an asthma exacerbation during screening may be re-screened 4 weeks after complete recovery from the exacerbation.
13. Patients who have had a respiratory tract infection or asthma worsening within 4 weeks of Visit 1. Patients who experience a respiratory tract infection or asthma worsening during screening may be re-screened after 4 weeks after recovery.
14. Patients with any chronic condition of the respiratory tract which in the opinion of the investigator may interfere with study evaluation or optimal participation in the study.
15. Patients with a history of chronic lung disease other than asthma, including (but not limited to) chronic obstructive pulmonary disease (as defined by Global Initiative For Chronic Obstructive Lung Disease (GOLD) standards), bronchiectasis, (non-clinically significant bronchiectasis may be allowed provided recent (within 3 months prior to Visit 101) computed tomography (CT) scan proof is available), sarcoidosis interstitial lung disease, cystic fibrosis, and tuberculosis.
16. Patients with a history of conditions other than asthma or allergic rhinitis that could result in elevated eosinophils (e.g., hypereosinophilic syndromes, Churg-Strauss Syndrome,

- eosinophilic esophagitis). Patients with known parasitic infestation within 6 months prior to Visit 1 are also excluded.
17. Patients with uncontrolled diabetes having an hemoglobin A1c (HbA1c) test result  $\geq 8\%$  at the Visit 1 laboratory test.
  18. Patients who have a clinically significant laboratory abnormality at the Visit 1 laboratory test including (but not limited to):
    - Total white blood cell count  $< 2500$  cells/ $\mu\text{L}$ ;
    - Aspartate aminotransferase (AST) or alanine aminotransferase (ALT)  $> 2.0$  X ULN or total bilirubin  $> 1.3$  X ULN;
    - Estimated Glomerular Filtration Rate (eGFR) by the modification of diet in renal disease study (MDRD) equation or Bedside Schwartz equation  $< 55$  mL/minute/ $1.73$  m^2.

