### **6.5.4 Laboratory evaluations**

A central laboratory will be used for analysis of all specimens detailed in this section. Details on the collections, shipment of samples and reporting of results by the central laboratory are provided to investigators in the laboratory manual.

Clinically notable laboratory findings are defined in [Appendix 1](#).

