#### 6.5.4.3 Urinalysis

Urine for urinalysis and urine chemistry will be collected according to the collection schedule in Table 6-1. **All samples for urinalysis and urine chemistry will be sent to the central laboratory for analysis.** The urinalysis evaluation by the central laboratory will include a urine dipstick for specific gravity, protein, glucose, leukocytes and blood and, if required, a microscopic examination. Urine chemistry and microscopic examination of the urine will be performed by the central laboratory as delineated in Table 15-1 “Specific Renal Alert Criteria and Actions” in Section 7.4 “Renal Safety Monitoring” of this protocol”. Other reflex testing will be performed as outlined in the laboratory manual.

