## 7.4 Renal safety monitoring

The following two categories of abnormal renal laboratory values have to be considered during the course of the study:

- Serum event:
  - Confirmed (after  $\geq 24$  hours) increase in serum creatinine (sCr) of  $\geq 25\%$  compared to baseline during normal hydration status.
- Urine event
  - Albumin-creatinine ratio (ACR)  $\geq 1\text{g/g}$  or  $\geq 100\text{ mg/mmol}$ .

- Protein-creatinine ratio (PCR)  $\geq 1\text{g/g}$  or  $\geq 100\text{ mg/mmol}$ .

Every renal laboratory trigger or renal event as defined in [Table 15-1](#) should be followed up by the investigator or designated personnel at the trial site as summarized in [Appendix 3](#).

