#### **9.5.2.4 Laboratory data**

All laboratory data will be listed with abnormal values flagged. The laboratory values and the change from baseline for continuous laboratory parameters will be summarized at each visit. A frequency table of results for categorical laboratory parameters will be produced for the whole study duration.

Shift tables relative to the normal reference ranges will be used to summarize the change from baseline to post-baseline for each laboratory parameter. For each laboratory parameter, the patients will be classified into one of the four mutually exclusive groups (low, normal, high, and low + high).

For selected laboratory parameters, the number and percentage of patients with newly occurring or worsening laboratory abnormalities meeting the clinically notable criteria will be summarized by laboratory parameter at any time-point over the treatment period, considering all post-baseline data from scheduled, unscheduled and premature discontinuation visits. Patients with any newly occurring or worsening value meeting the clinically notable criteria will be counted under the applicable criteria.

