## **13 Appendix 1: Clinically notable laboratory values and vital signs**

The central laboratory will flag laboratory values falling outside of the normal ranges on the central laboratory reports. Investigators are responsible for reviewing these abnormal values for clinical significance, signing the laboratory reports to indicate their review, and reporting values considered clinically significant in the appropriate electronic case report form (eCRF).

Any clinically significant abnormal laboratory value should be evaluated and followed-up by the investigator until normal or a cause for the abnormality is determined.

**See [Appendix 2](#) for specific liver event and laboratory test trigger definitions and follow-up requirements. See [Appendix 3](#) for specific renal alert criteria and actions.**

For electrocardiograms (ECGs), a notable QTc value is defined as a QTcF (Fridericia) interval of  $\geq 450$  msec for males or  $\geq 460$  msec for females – all such ECGs will be flagged by the Central contract research organization (CRO) and require assessment for clinical relevance and continuance of the patient by the Investigator.

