## 15 Appendix 3: Specific Renal Alert Criteria and Actions

**Table 15-1 Specific Renal Alert Criteria and Actions**

Serum Event	
Serum creatinine increase 25 – 49% compared to baseline	Confirm 25% increase after 24-48h Follow up within 2-5 days
Acute Kidney Injury: Serum creatinine increase $\geq$ 50% compared to baseline	Follow up within 24-48h if possible Consider study treatment interruption Consider patient hospitalization /specialized treatment
Urine Event	
Albumin-creatinine ratio (ACR) $\geq$ 1g/g or $\geq$ 100 mg/mmol; Protein-creatinine ratio (PCR) $\geq$ 1g/g or $\geq$ 100 mg/mmol	Confirm value after 24-48h Perform urine microscopy Consider study treatment interruption / or discontinuation
For all renal events:	

Document contributing factors in the CRF: co-medication, other co-morbid conditions, and additional diagnostic procedures performed
 
Monitor patient regularly (frequency at investigator's discretion) until either:
 
Event resolution: sCr within 10% of baseline or protein-creatinine ratio within 50% of baseline, or
 
Event stabilization: sCr level with <math>\pm</math>10% variability over last 6 months or protein-creatinine ratio stabilization at a new level with <math>\pm</math>50% variability over last 6 months.
	

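### SAP Table 6-4-2 counts creatinine only against an absolute 176.8 µmol/L and has no ACR or PCR criterion, so it gives no by-arm laboratory counts at the protocol's renal alert levels

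*SAP*

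**What the plan says.** Protocol 6.5.4 states that "Clinically notable laboratory findings are defined in" Appendix 1. That appendix sets no limit for creatinine, ACR or PCR; it sends the reader to Appendix 3 "for specific renal alert criteria and actions". Protocol 9.5.2.4 says that, for selected parameters, "the number and percentage of patients with newly occurring or worsening laboratory abnormalities meeting the clinically notable criteria will be summarized".

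Appendix 3 (Table 15-1) has two creatinine tiers, 25-49% and 50% or more above baseline, the second headed acute kidney injury. It also has a urine tier, ACR or PCR of at least 1 g/g or 100 mg/mmol. For the lower creatinine tier the action is "Confirm 25% increase after 24-48h". Protocol 7.4 defines the serum event as a rise of at least 25%, confirmed after 24 hours or more, "compared to baseline during normal hydration status".

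SAP 2.7.3.3 counts patients whose new or worsened on-treatment values meet Table 6-4-2, "Clinical notable criteria for selected laboratory tests". Creatinine is in that table with the single bound 176.8 µmol/L. The other kidney-related rows are BUN/urea and dipstick protein at 2+ or more. SAP 2.7.5 adds a by-treatment summary and a listing of renal event overview data, without naming thresholds or the data source.

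**The concern.** The SAP chose creatinine for the notable-value count but gave it a bound unrelated to the patient's own baseline, while the protocol's renal alerts for creatinine are all relative to baseline. A drug that raised creatinine moderately in a small share of patients could show few or no creatinine cases in that table. The reader would then have to look for the signal in the renal event summary or at the extremes of the change-from-baseline summaries. ACR and PCR have no threshold count from laboratory data at all. At stake is how readily a moderate renal imbalance between arms would be seen.

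**Working it through.** **Inputs.** Creatinine bound B = 176.8 µmol/L (SAP Table 6-4-2). Alert tiers of 25-49% and 50% or more (protocol 7.4 and Table 15-1). The documents give no distribution of baseline creatinine, so 60 to 110 µmol/L is an assumed range for illustration. The SAP does not derive the 176.8, so there is no figure of the plan's own to reproduce.

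**Baseline from which a given rise reaches the bound**, B / (1 + rise):
- 25% rise: 176.8 / 1.25 = 141.4
- 49% rise: 176.8 / 1.49 = 118.7
- 50% rise: 176.8 / 1.50 = 117.9
- 100% rise: 176.8 / 2 = 88.4

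At a baseline of 117.8, a 50% rise gives 176.7. That is below the bound whether the bound is read as above or at-or-above, so no rise under 50% from 117.8 or lower can be counted.

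**Rise needed to be counted**, B / baseline − 1, over the assumed range:

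| Baseline (µmol/L) | Value after a 49% rise | Rise needed to reach 176.8 |
|---|---|---|
| 60 | 89.4 | 194.7% |
| 80 | 119.2 | 121.0% |
| 90 | 134.1 | 96.4% |
| 100 | 149.0 | 76.8% |
| 110 | 163.9 | 60.7% |

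The whole 25-49% tier is uncounted across this range, and so is the lower part of the tier of 50% or more. A doubling from 80 to 160 is not counted; a doubling from 90 to 180 is. Exclusion criterion 18, which uses "Estimated Glomerular Filtration Rate (eGFR) by the modification of diet in renal disease study (MDRD) equation" or the Bedside Schwartz equation with a limit of 55, restricts how many patients start with high creatinine.

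**What else shows these alerts by arm.**
- SAP 2.7.5 does not say where its data come from. Protocol 7.3 uses the parallel term for liver CRF pages, protocol 7.4 assigns follow-up to site staff, and Table 15-1 asks for CRF documentation. CRF recording is the natural inference.
- Table 6-1 schedules on-treatment chemistry only at the treatment discontinuation visit (TD) and Visit 299. A rise first seen at Visit 299 must be confirmed afterwards, and renal event monitoring is not scheduled at Visit 301, although liver event monitoring is.
- SAP section 4 drops the laboratory shift tables that protocol 9.5.2.4 had planned.
- SAP 2.7.3.1 and 2.7.3.2 summarise worst-case values and worst-case change from baseline by arm, but do not count patients at the alert levels.

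Liver safety has both an event summary (SAP 2.7.6) and a laboratory table with several thresholds (Table 6-4-3). Renal safety has only the event summary.

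**The case against.** The strongest reply is that no promise is broken. Protocol 9.5.2.4 commits only to selected parameters, and Table 15-1 is a table of alerts and actions; no text says its thresholds are the notable criteria. The SAP also states that some parameters have no notable criteria. This stands: a reader might infer that the SAP breaches the protocol, and the documents do not support that. It is a choice of analysis, though one that section 4 of the SAP does not list as a change.

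A second reply is that confirmed events are the better measure, since the protocol requires repeat testing and normal hydration, and SAP 2.7.5 reports them by arm. That is a good reason to keep 2.7.5. It does not supply a count from laboratory data.

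Two further readings go too far. One is that the notable-value table misses every patient with an ACR or PCR alert. The dipstick protein row may flag some of the same patients; what is absent is a count at 1 g/g. The other is that sites will under-record renal events. Table 6-1 asks sites to review laboratory results against protocol 7.4, and protocol 6.5.4.3 says "Urine chemistry and microscopic examination of the urine will be performed by the central laboratory as delineated in" Table 15-1. CRF dependence is an inference, and nothing shows that recording would fail.

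Finally, the worst-case summaries may reveal extreme values, and clinically significant laboratory changes are reportable as adverse events. Both soften the gap. Neither gives patients per arm at the alert levels.

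**Conclusion.** The point holds as a minor gap in safety reporting. The creatinine arithmetic depends only on the two documents' thresholds: rises under 50% from a baseline of 117.8 µmol/L or lower cannot appear in the notable-value count, and many larger ones cannot either. The illustration over 60 to 110 µmol/L rests on an assumed range. The share of patients affected, and whether any imbalance would in fact be hidden, cannot be determined from the documents. That the 2.7.5 summary depends on CRF entries is well supported but not stated. Efficacy, alpha and power are unaffected.

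**What to change.** In SAP 2.7.3.3 and Table 6-4-2, add three by-arm rows from on-treatment central-laboratory data (TD, Visit 299 and unscheduled samples, up to 7 days after last intake):

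1. creatinine increase from baseline of 25% or more;
2. creatinine increase from baseline of 50% or more;
3. newly occurring ACR or PCR of at least 1 g/g (100 mg/mmol).

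Label them as unconfirmed laboratory threshold crossings, to keep them apart from protocol-defined renal events. Keep the 176.8 µmol/L row and the 2.7.5 summary, and state in 2.7.5 that renal events are those of protocol 7.4 and Table 15-1.

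The cost is SAP wording and three table rows, with no new data collection. The downside is that some transient, unconfirmed rises will be counted in both arms, and two renal counts will sit side by side, which is why the label matters.
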